## 1 Trial Registration/Protocol Summary

Information	
EudraCT number:	N/A
Date of registration:	
ClinicalTrials.gov:	NCT05251805
Official Title:	Phase I clinical trial evaluating the safety and feasibility of bone marrow aspiration from ribs during thoracic surgery
Study Phase/Type:	Phase I clinical trial
Condition:	Lung cancer
Objectives:	Evaluate the safety and feasibility of bone marrow aspiration during thoracic surgery
Investigational Product or Medical Device:	None
Interventions:	
 
1. Pre-operative blood sample collection
 
2. Costal bone marrow aspiration
 
3. Lung tumor and adjacent tissue sampling
 

Endpoints:	
 
1. Safety: the occurrence of complications
 
2. Feasibility: Obtain a minimum of <math>2 \times 10^6</math> Lin CD34+ Hematopoietic Stem and Progenitor Cells (HSPCs) to allow single cell RNA sequencing (<math>10^6</math>), bone marrow cultivation in vitro (<math>5 \times 10^5</math> cells per culture) and transplantation in immuno-deficient mice (<math>10^5</math> cells per injection).
 

Study population:	Lung cancer patients undergoing thoracic surgery
Number of patients:	10
Overview of study design:	Phase I feasibility trial
Statistical Considerations:	None
Sponsor:	UZ Brussel
Inclusion Criteria:	Confirmed or suspected lung cancer patients undergoing thoracic surgery
Exclusion Criteria:	
 
1. ASA <math>\geq 3</math>
 
2. Bleeding disorders
 

Target Date of first enrolment:	01/10/2022
Target sample size:	10

## **2 Protocol Version History**

Version No.	Release Date	Summary of Changes
V1	20 April 2022	-
V1.1	28 June 2022	Upon request of the EC: made some minor changes concerning the reporting of SAE's and added an explanation on the multidisciplinary aspects of the research project.

## **4 List of Abbreviations**

ICI: immune checkpoint inhibitors

NSCL: non-small cell lung cancer

EU: European Union

LuCE: Lung Cancer Europe

PD-L1: programmed death-ligand 1

TME: tumor micro-environment

BMN: bone marrow niche

HSPCs: hematopoietic stem and progenitor cells

LMCT: Laboratory for Molecular and Cellular Therapy

PBS: phosphate buffered saline

## **5 Introduction**

### 5.1 Overview of Disease Pathogenesis

Non-small cell lung cancer (NSCLC) remains the leading cause of cancer-related deaths worldwide, with a staggering 2.21 million new cases in 2020 alone. For patients with stage I and stage II disease, surgical resection is the primary modality of treatment. However, only 20-30% of lung cancer patients are suitable for curative treatment (surgery versus stereotactic radiotherapy) at the time of diagnosis. Moreover, following surgery, the risk of recurrence during the first 4-year ranges from 6% to 10% per person per year but decreases thereafter to 2%. Current progress in the field of **antitumor immunotherapy** is based on the capacity of effector T cells to recognize and kill cancer cells specifically. As progressing tumors often master skills to restrict T-cell mediated killing via upregulation of immune checkpoint molecules, immune checkpoint inhibitors (ICIs) were designed to ameliorate antitumor immunity. Today, the latter represents a first-line treatment option for advanced NSCLC patients with curative potential. Unfortunately, up to **75% of patients currently do not respond** to ICIs, suggesting that lung tumor cells master more skills to mislead effector T cells than upregulating immune checkpoint molecules alone, highlighting the ongoing medical need to develop additional/alternative (immune)therapeutics that enhance the overall survival rate of ICI-treated NSCLC patients.

## 5.2 Epidemiology

Lung cancer is the fourth most diagnosed cancer, affecting more than 312.000 people every year in the European Union (EU). Cigarette smoking is the major cause of lung cancer, with around 80-90% of all lung cancer attributable to tobacco. In men, lung cancer is the second most diagnosed cancer. In women, lung cancer is the third most frequent cancer. However, this gender gap is closing. Lung cancer survival is poor, although new treatments lead to a slightly better prognosis. The overall 5-year survival is around 13% since diagnosis.

## 5.3 Current Treatments

1. Stage I disease: surgery or stereotactic radiotherapy in patient unfit for surgery
2. Stage II disease: surgery followed by adjuvant chemotherapy
3. Stage III disease: chemoradiotherapy
4. Stage IV disease: chemotherapy, targeted therapy, and immunotherapy. Immunotherapy is used as a first-line treatment in NSCLC patients without driver mutations whose tumors express PD-L1 (programmed death ligand-1) at levels of 50% or greater.

## 5.4 Study Rationale and Purpose

In general, antitumor immunotherapy tends to spark the patients' own tumor-specific effector T cells to multiply, recognize and kill tumor cells. Yet, a typical characteristic of immunotherapy-resistant (lung) tumors' deceptive gambit, is their molding of an effector T-cell hostile **tumor microenvironment (TME)**. The latter comprises cellular, molecular, vascular, and physical **barriers** for effector T cells which hamper effective tumor cell killing. With regard to the cellular barriers, we and others have appointed a leading role to the immunosuppressive myeloid cells. These myeloid cells represent a heterogeneous group of subsets with embryonic origin (macrophages) and/or hematopoietic origin (dendritic cells, macrophages, granulocytes, mast cells, and platelets), suggesting that the **bone marrow niche (BMN)** is involved in the creation of an immunosuppressive T-cell hostile TME. Moreover, this niche has been shown to aid in pre-metastatic niche formation while it has also been proposed as a supportive **hideout** for disseminated cancer cells, as reported by the detection of Epcam+ CD45 disseminated cancer cells in 43,5% of sternal aspirated BM samples from 62 NSCLC patients. Nevertheless, as BM aspiration is a painful process and therefore, unlike blood drawing not routinely performed, it remains a tremendously **understudied niche in solid cancers**.

Next to the fundamental information that BMN investigation would deliver to ameliorate our understanding of NSCLC progression and resistance to (immuno)therapy, bone marrow represents an extremely valuable biomaterial for preclinical onco-immunology research. More specifically, the Lin- CD34+ hematopoietic stem (and progenitor) cells or **HSPCs** have been used to **generate humanized mice** by transplanting total body irradiated mice with human bone marrow. Anti-tumor immunotherapy (and research thereof) relies on histocompatible cell-to-cell interactions between the immune system, tumor cells and their TME. Hence, humanized patient-derived xenograft models in which the immune system and tumor are derived from the same patient, a.k.a. 'murinized patients', represent the ultimate model to study human tumor immunology and evaluate innovative immunotherapies.

To study the BMN and autologous tumor-bone marrow interactions, we want to collect **blood, bone marrow and lung tissue of 10 lung cancer patients**.

1) This pilot trial is designed to **evaluate the feasibility and safety of obtaining bone marrow upon costal aspiration** during surgery. The rationale for using rib bone marrow aspiration is the easily accessible localization due to trocar placement (in minimally invasive surgery) or during thoracotomy. Previous trials demonstrated the feasibility of micro-metastasis detection in rib marrow aspiration. This procedure was safe without any documented adverse events for patients. We hypothesize that we can use this technique to obtain sufficient bone marrow-derived HSPCs (which represent only 0,1% of the total bone marrow fraction) for *ex vivo* single-cell evaluation, optimization of a 3D BMN platform^15 and preclinical *ex/in vivo* assessment in patient-derived organoids and murine xenograft models. The use of rib marrow eliminates the need for extra incision as incisions used for trocar placement or thoracotomy will be used. We

hypothesize that the patient will not experience extra discomfort from this technique since every patient undergoing thoracic surgery is treated according to the ERAS protocols with a major emphasis on pain control.

2) If the feasibility and safety of bone marrow aspiration are confirmed by this pilot trial, we plan to conduct a large-scale study in which we will collect and bank blood, bone marrow and tumor per NSCLC patient. With this unique autologous biological material collection, we aspire to conduct innovative research into the current resistance mechanisms of NSCLC to immunotherapy via at least two ongoing research projects:

- a) **X-talk project** with the hypothesis: 'The bone marrow niche of NSCLC patients withholds invaluable information about tumor-installed resistance mechanisms to immunotherapy. By deciphering this information, we aspire to serve the diagnostic and therapeutic field.'
- b) **RADar project** with the aim to answer the following research questions: 1) can we efficiently deliver RADars specifically to human lung tumor cells? and 2) will RADar delivery result in tumor cells' sensitivity to and killing by patient-specific human T cells? To be able to answer these questions in a relevant way, we opt for two meticulous human(ized) immunological models namely:
  - an ***in vitro* Predixoid platform** in which NSCLC organoids are grown as TME-on-a-chip.
  - '**murinized patients**', in which patient-derived NSCLC cells or organoids are engrafted intrathoracic into immunodeficient mice to generate orthotopic lung cancer patient xenografts. Next, we will optimize the generation of humanized mice, transplanted with NSCLC patient-derived HSPCs and subsequent autologous and orthotopic NSCLC tumor engraftment to generate 'murinized patients'.

Hence, by exploiting patient-derived material, we aspire to perform **more clinically relevant fundamental and translation research**, especially as the use of both platforms will allow us to take **inter-patient-heterogeneity** into account (unlike immortalized lung tumor cell lines).

The PI of this feasibility trial, [name] (MD), is an anesthesiologist. He has written the study protocol in close cooperation with [name] (MD, PhD) and [name] (PhD). In conjunction with [name] (MD) he will include the patients in this trial, attend to the patient during and after the surgical procedure and perform the bone marrow aspiration.

## 5.5 Rationale for Study Design

This trial is a feasibility trial evaluating the possibility to obtain bone marrow-derived HSPCs by bone marrow aspiration from ribs.

## 5.6 Rationale for Dose and Regimen/Schedule Selection

Not applicable

# **6 Study Schematic and Schedule of Activities**

## 6.1 Study Schematic

1. Patient screening and informed consent
2. Collection of samples:
  - a. Blood sample collection during pre-operative blood collection
  - b. Bone marrow aspiration during thoracic surgery
  - c. Lung tumor and adjacent tissue true cut on removed lung tissue
3. Observation of adverse events during the first 30 days following surgery
4. Processing of obtained tissue at LMCT

## 6.2 Primary Objective

The safety and feasibility of rib bone marrow aspiration during thoracic surgery

### 6.3 Secondary Objectives

None

### 6.4 Endpoints

1. Safety: the occurrence of complications
2. Feasibility: Obtain a minimum of  $2 \times 10^6$  Lin- CD34+ HSPCs to allow single cell sequencing ( $10^6$ ), bone marrow cultivation ( $5 \times 10^5$  cells per culture) and transplantation in immunodeficient mice ( $10^5$  cells per injection).

## **7 Investigational Plan**

### 7.1 Overall Study Design

- 1) This trial is a phase I feasibility trial. It is designed to evaluate the feasibility and safety of obtaining bone marrow upon costal aspiration during surgery.
- 2) If feasibility and safety of rib bone marrow aspiration are confirmed in this pilot trial, a large-scale study will be started to optimize and conduct fundamental and translational research via the X-talk project and RADar project (see details under 5.4, page 9).

### 7.2 Study Duration for Subjects

#### 7.2.1 *Screening*

All patients undergoing thoracic surgery (by minimally invasive technique or by thoracotomy) will be screened for their eligibility by the principal investigator.

#### 7.2.2 *Treatment Period*

- a. Blood sample collection during pre-operative blood collection
- b. Bone marrow aspiration during thoracic surgery – no additional incisions will be made
- c. Lung tumor collection – only tumor not used for diagnostic purpose

#### 7.2.3 *Unscheduled Visit(s)*

All patients will be hospitalized the day before surgery and between 5-7 days following surgery. This is standard practice for all patients undergoing thoracic surgery in our department. No unscheduled visits will be necessary

#### 7.2.4 *Early Study Termination*

The study will be closed prematurely if 2 patients experience a grade 3 adverse event directly related to the bone marrow aspiration

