#### 7.2.5 *End of Study*

The study will end once 10 study patients have been included. We foresee that the end will be scheduled for 31st of December 2025.

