### 10.3 Known Undesirable Effects of costal rib aspiration

- Pain
- Bleeding
- Infection

In a survey of members of the British Society of Haematology reported in 2003, there were 26 adverse events, including one fatality, out of an estimated total of 55,000 bone marrow biopsy procedures (0.05 percent). A follow-up survey of this group, reported in 2006 involving 20,323 procedures, resulted in the reporting of 15 adverse events (0.07 percent). Previous research evaluating the feasibility to detect disseminated tumor cells in bone marrow aspirate from the ribs couldn't identify any adverse events related to the bone marrow aspiration.

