#### 11.1.7 Early Termination

The trial will be ended prematurely if grade 3 (or higher) adverse events occur in 2 patients

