#### 12.1.4 *Immediate Reporting*

In the occurrence of adverse events of grade 3 or higher related to the trial procedure, the ethical committee will be contacted. In the occurrence of 2 adverse events of grade 3 or higher the trial will be prematurely discontinued.

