## **13 Data Collection and Management**

### 13.1 Monitoring

#### 13.1.1 Composition of data monitoring committee

Given the low number of included patients, the low risk of serious adverse events, and the single-center set-up, no external data monitoring committee is foreseen.

During patient recruitment and up to 3 months following the inclusion of the last study patient, the principal investigator and the co-investigators will review and confirm all data on a 3-monthly basis during a teleconference. All data (outcome, duration of hospital stay, complications) will be gathered on red-cap. No statistical analyses will be performed.

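### The early-termination wordings disagree with each other, and none says what happens to inclusion after a first aspiration-related grade 3 or higher event, including a death

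*Protocol*

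**What the plan says.** Early termination is described in four places in the protocol.

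- Section 7.2.4: "The study will be closed prematurely if 2 patients experience a grade 3 adverse event directly related to the bone marrow aspiration".
- Section 11.1.7: "The trial will be ended prematurely if grade 3 (or higher) adverse events occur in 2 patients".
- Section 12.1.4: "In the occurrence of 2 adverse events of grade 3 or higher the trial will be prematurely discontinued".
- Section 12.2.2 repeats 12.1.4 and adds that the ethics committee is notified.

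For a single event, sections 12.1.4 and 12.2.2 say: "In the occurrence of adverse events of grade 3 or higher related to the trial procedure, the ethical committee will be contacted". Section 12.1.3 has every grade 3 or higher event reported as serious. Grading is by Clavien-Dindo, in which grade 5 is death (section 12.1.1).

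On oversight, section 13.1.1 cites the small number of patients and then "the low risk of serious adverse events, and the single-center set-up, no external data monitoring committee is foreseen". The investigators review the data every three months. Section 13.1.2 sets an interim look after five patients, limited to the size of the blood sample, the amount of marrow, and whether it suffices for the laboratory work.

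On size and pace, section 7.2.5 says "The study will end once 10 study patients have been included", and patients are taken consecutively.

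On risk, section 10.3 cites two surveys of bone marrow biopsy. The first reports 26 adverse events, one of them fatal, in an estimated 55,000 procedures. The second is described as "involving 20,323 procedures, resulted in the reporting of 15 adverse events (0.07 percent"). The section adds that earlier rib-aspirate work found no related adverse events, without giving a denominator.

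**The concern.** Section 10.1 calls the aspiration experimental and the rib literature scarce. The marrow is taken for research. The investigator who includes the patients also performs the aspiration and attends to them afterwards (section 5.4). In that setting the early-termination rule carries most of the formal protection, and it has two weaknesses.

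First, the same pair of events can close the trial under one section and not under another. Second, the protocol goes from one related serious event straight to closure at two, with nothing stated in between except a contact. If the first event were a death, no passage says whether the next patient may be included before anyone has reviewed it.

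At stake is the safety of the remaining patients. So is the meaning of a completed trial, because sections 5.4 and 7.1 make a large-scale study depend on safety being confirmed here.

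**Working it through.** **1. The four wordings side by side**

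| Section | Counts | Grade | Relatedness |
|---|---|---|---|
| 7.2.4 | 2 patients | 3 (higher grades not named) | directly related to the aspiration |
| 11.1.7 | 2 patients | 3 or higher | not required |
| 12.1.4 | 2 events | 3 or higher | not repeated in the closing sentence |
| 12.2.2 | 2 events | 3 or higher | not repeated in the closing sentence |

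Three test cases show the disagreement.

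- Two related deaths close the trial under 11.1.7, 12.1.4 and 12.2.2. Read literally, 7.2.4 does not count them.
- Two patients with grade 3 complications of the lung surgery itself close it under 11.1.7 but not under 7.2.4.
- Two related grade 3 events in one patient close it under 12.1.4 and 12.2.2 but not under 7.2.4 or 11.1.7.

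Section 12.2.1 adds a further standard of relatedness, namely events that might be related.

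**2. The protocol's own risk figures**

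26/55,000 = 0.047% (stated as 0.05%) and 15/20,323 = 0.074% (stated as 0.07%). Both reproduce.

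**3. What those rates imply in ten patients**

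With per-patient rate q, P(at least 1) = 1 − (1 − q)^10 and P(at least 2) = 1 − (1 − q)^10 − 10q(1 − q)^9.

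- One procedure per patient: P(at least 1) = 0.47% to 0.74%; P(at least 2) = 0.0010% to 0.0024%.
- Six punctures per patient (assumption: two at each of three trocar sites, each counted as a procedure). At the higher survey rate q = 1 − (1 − 0.000738)^6 = 0.44%. Across the two rates, P(at least 1) = 2.8% to 4.3% and P(at least 2) = 0.04% to 0.09%.

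The exact two-sided 95% lower limit is 0.25% for 1 event in 10, above both survey rates. For 1 event in 60 punctures it is 0.042%, below both.

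**4. How often a two-case rule closes the trial**

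Inputs: n = 10, related grade 3 or higher events counted once per patient, patients independent. The true rates are assumptions, because the protocol names no unacceptable rate. At 10%: 1 − 0.9^10 − 10 × 0.1 × 0.9^9 = 1 − 0.349 − 0.387 = 0.264.

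| True rate per patient | At least 2 (closes) | At least 1 | Exactly 1 (difference) |
|---|---|---|---|
| 1% | 0.4% | 9.6% | 9.1% |
| 5% | 8.6% | 40.1% | 31.5% |
| 10% | 26.4% | 65.1% | 38.7% |
| 20% | 62.4% | 89.3% | 26.8% |
| 30% | 85.1% | 97.2% | 12.1% |

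The differences use unrounded values. The last column is the chance that the trial runs to ten patients with one related serious event and no stated action on inclusion. The closing column slightly flatters the rule, since a second case in the tenth patient protects nobody. The chance of two cases among the first nine patients is 23%, 56% and 80% at rates of 10%, 20% and 30%.

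**The case against.** The strongest reply is that a closing boundary ought to be almost unreachable when the risk is as low as expected, because that avoids false stops. On this view a 0.002% chance of two events at the survey rate is a virtue. That stands. A reader might infer that the two-case boundary conflicts with the risk figure in section 10.3. The documents do not support this. The protocol never links the survey rates to the boundary, and section 13.1.1 uses low risk, among other grounds, only to explain the absence of an external committee.

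A reader might also infer that one related event would already contradict the stated low risk. That holds if each patient counts as one procedure. It fails on the two-sided limit if each of six punctures counts. The surveys also concern a different setting and report adverse events without Clavien-Dindo grades.

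It can further be said that silence about a hold is not a statement that inclusion continues, and that section 12.1.4 is headed as immediate reporting. This is fair. The protocol does not order the next aspiration after a death; it leaves the matter open.

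Finally, the pace is slow. From the target first enrolment on 1 October 2022 to 31 December 2025 is 39 months, or 3.9 months per patient if accrual is even, so a three-monthly review would often fall between patients. That lowers the practical risk. But consecutive inclusion does not guarantee even spacing, and no review in the protocol is tied to inclusion.

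**Conclusion.** The point holds in this form: the four closing rules contradict one another on grade, relatedness and counting unit, and the step after a first related grade 3 or higher event is fixed only as a contact with the ethics committee. Neither the interim look nor the investigators' review fills that gap.

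For related events counted per patient, a two-case rule closes the trial with probability 26%, 62% or 85% at true rates of 10%, 20% or 30%. These figures rest on independent patients and assumed rates. They do not describe 11.1.7, which does not require relatedness and would close the trial more often, nor the event-counting wordings when one patient has two events.

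It would go too far to say that a trial with one related death would be declared safe. The protocol sets no criterion for confirmed safety in either direction.

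**What to change.** 1. Replace the wordings in 7.2.4, 11.1.7, 12.1.4 and 12.2.2 with one rule, stated once and cross-referenced. It should cover grades 3 to 5, use one standard of relatedness, and say whether patients or events are counted. The sponsor sets the closing boundary itself.
2. Make the contact already required in 12.1.4 and 12.2.2 operative as trial conduct. For example: *After a first event of grade 3 or higher related to the aspiration, a death included, no further patient is included until the ethics committee has reviewed the event.*

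This adds a sentence and merges existing text. It changes no patient's treatment and needs no new committee. The downside is a possible pause in inclusion of some weeks, small against 39 planned months. If the survey rates apply with one procedure per patient, the hold would be triggered in under 1% of such trials (about 3% to 4% with six punctures). At a true rate of 10% it would be triggered in 65%. Printing the stopping probabilities beside the rule would be informative, but without the hold it would change nothing.

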## **10 Interventions/Treatment**

### 10.1 Intervention

- a. Blood sample collection during pre-operative blood collection  
A total of 12 ml will be collected
- b. Bone marrow aspiration during thoracic surgery  
Following the surgical intervention, bone marrow aspiration will be performed through the incisions made for the thoracic procedure. The ribs lying directly above and below the trocar incision will be exposed. A bone marrow needle will be advanced into the periost until the needle tip reaches the bone marrow. After removing the stylet a 2ml syringe will be attached to the aspiration needle and 0.5ml to 2ml of bone marrow will be aspirated before removing the needle. This procedure will be repeated twice for every trocar site, for a maximum of 3 trocar sites, or until 5ml of bone marrow aspirate is obtained. This part of the trial is experimental. Literature on rib bone marrow aspiration is scarce but good results are obtained. The procedures does not seem to be correlated with major AE.
- c. Lung tumor and adjacent healthy tissue collection – only tumor not used for diagnostic purposes.  
All surgical samples will be analyzed by our anatomopathological department. Viable and fresh material, obtained via true cut biopsy on the excised tissue and not used for the diagnostic purposes, will be collected by the LMCT.

All samples (blood, bone marrow, and fresh tumor tissue), will be transferred to the LMCT for immediate processing of viable cells (within 2 hours after isolation) and subsequent cultivation and/or cryopreservation for later usage.

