#### 11.1.5 End of Study

Adverse events will be followed up to four weeks postoperatively.

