#### 12.1.2 *Reporting Period*

All adverse events related to the bone marrow aspiration will be evaluated and classified by their treating physician. Adverse events occurring during the first postoperative month (30 days) will be registered.

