## 12.2 Suspected Unexpected Serious Adverse Events (SUSAR)

### 12.2.1 Definitions

All adverse events of grade 3 or higher (according to the Clavien Dindo classification) that might be related to a trial related procedure will be reported as a serious adverse event

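### The only safety stopping rule is given in three conflicting forms (Protocol 7.2.4, 11.1.7, and 12.1.4 with 12.2.2), and nothing says which one governs

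*Protocol*

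**What the plan says.** The Protocol states the stopping rule four times.

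- Section 7.2.4: "The study will be closed prematurely if 2 patients experience a grade 3 adverse event directly related to the bone marrow aspiration".
- Section 11.1.7: "The trial will be ended prematurely if grade 3 (or higher) adverse events occur in 2 patients".
- Section 12.1.4: "In the occurrence of 2 adverse events of grade 3 or higher the trial will be prematurely discontinued". The sentence before it says that the ethics committee is contacted about grade 3 or higher events related to the trial procedure.
- Section 12.2.2 repeats the section 12.1.4 rule and adds that the ethics committee is notified.

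Three other places bear on how these are read. Section 12.1.1 grades events on the Clavien-Dindo scale, where grade 4 is life-threatening and grade 5 is death. Section 12.1.2 has the treating physician evaluate events related to the aspiration, and then says that adverse events in the first 30 days are registered, without repeating that limit. Section 12.1.3 makes every event of grade 3 or higher a serious adverse event, related or not.

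**The concern.** A stopping rule has to say what is counted, at what severity and with what link to the intervention. Here each of these changes from one section to another, and no section is given precedence.

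Relatedness matters especially in this trial. According to section 10.1, "bone marrow aspiration will be performed through the incisions made for the thoracic procedure", and section 10.3 lists pain, bleeding and infection as the known undesirable effects. The lung operation can cause the same events at the same site. Whether unrelated complications count can therefore decide whether a 10-patient study is closed.

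There is no other safeguard that would settle the matter. Section 13.1.1 foresees no external monitoring committee, and the interim look after 5 patients in section 13.1.2 concerns sample adequacy only. The investigators must apply the rule from the text, and the text gives them three.

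**Working it through.** The Protocol gives no operating characteristic for the rule, so there is no figure to reproduce. The check is to set the three forms side by side and apply each to the same events.

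**Elements of each form, as written**

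| Section | Unit | Grade | Relatedness |
|---|---|---|---|
| 7.2.4 | 2 patients | 3 | directly related to the aspiration |
| 11.1.7 | 2 patients | 3 or higher | none stated |
| 12.1.4, 12.2.2 | 2 events | 3 or higher | none in the stopping sentence; may be carried over from the sentence before |

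**Does the trial stop?** The last two columns give sections 12.1.4 and 12.2.2 with and without relatedness carried over.

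| Pattern | 7.2.4 | 11.1.7 | 12.x, related only | 12.x, literal |
|---|---|---|---|---|
| A. Two patients, one related grade 4 event each | no | yes | yes | yes |
| B. One patient, two related grade 3 events | no | no | yes | yes |
| C. Two patients, one unrelated grade 3 event each | no | yes | no | yes |
| D. Two patients, one with a related and one with an unrelated grade 3 event | no | yes | no | yes |
| E. Two patients, one related grade 3 event each | yes | yes | yes | yes |

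All sections agree only in pattern E.

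**Most generous reading.** Suppose that 7.2.4 is taken to include grades 4 and 5, and that relatedness is understood in all four places. A then becomes yes throughout, and C and D become no throughout. B is unchanged: section 12 stops the trial, and 7.2.4 and 11.1.7 do not. The difference between patients and events therefore survives any reading.

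**If meeting any one form is enough.** The widest wording then governs, and the limit to directly related events in 7.2.4 has no effect. If instead 7.2.4 governs literally, two patients with related life-threatening or fatal events would not meet it.

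**Probabilities, for illustration only.** The chance that at least 2 of 10 patients are affected is 1 − (1−p)^10 − 10p(1−p)^9. The Protocol gives no rate of grade 3 or higher events from any cause. At assumed rates of 2%, 5%, 10% and 20%, the chance is 1.6%, 8.6%, 26.4% and 62.4%. At the 0.07% rate that section 10.3 cites for adverse events of bone marrow biopsy, it is about 0.002%. The any-cause figures depend wholly on the assumed rate, and the point does not rest on them.

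**The case against.** The strongest defence is that the four statements should be read together. Section 7.2.4 limits the rule to events from the aspiration, section 12.1.2 says "All adverse events related to the bone marrow aspiration will be evaluated and classified by their treating physician", and in 12.1.4 and 12.2.2 the stopping sentence directly follows one about related events. Section 11.1.7 omits a relatedness condition but does not say that events of any cause count. On this view patterns C and D disappear. It is a possible reading, but the text does not secure it: 11.1.7 has no neighbouring sentence to supply the limit, and 12.1.2 and 12.1.3 also register and define events without it. Pattern B remains in any case.

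It can also be said that nobody would run the trial on after two related deaths, so the missing words on higher grades in 7.2.4 are a slip. Probably so. That is a reason to correct the slip, not to leave it.

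Four stronger inferences are tempting, and the Protocol does not support them.

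- *That the trial is committed to an any-cause rule, or has a known sizeable chance of closing because of surgical complications.* Section 11.1.7 is silent on cause, and no rate is given. The binomial figures also overstate lost recruitment, because a second affected patient who is the tenth enrolled stops nothing. Counting the first nine patients only, 1.6% to 62.4% becomes 1.3% to 56.4%.
- *That the wording exposes patients to more risk.* Sections 11.1.7, 12.1.4 and 12.2.2 all include grades 4 and 5, and 11.1.7 leans towards stopping sooner.
- *That section 12.2.1 adds a further contradiction, since events "that might be related to a trial related procedure will be reported as a serious adverse event".* That is a reporting threshold. A wider threshold for reporting than for stopping is ordinary practice.
- *That the operators judge their own events.* Section 5.4 says that the investigators "attend to the patient during and after the surgical procedure and perform the bone marrow aspiration", while 12.1.2 gives classification to the treating physician. The Protocol does not say that these are the same people.

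**Conclusion.** The point stands as an internal inconsistency and should be fixed. The stopping rule exists in three forms that differ in unit (patients or events), grade (3, or 3 and above) and relatedness (direct, unstated, or implied at most), with none given precedence. As written they agree in one of the five patterns. On the most generous reading they still disagree when one patient has two related events.

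This rests on the wording alone and on no assumed event rate. The consequence is limited: no statistical analysis is planned (section 13.4), so no test, estimate or error rate changes. What is affected is whether the same events close the trial, in a study whose primary objective includes safety. This is not detail that could be left to a statistical analysis plan, because the Protocol itself fixes the rule and does so inconsistently.

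**What to change.** State one rule in section 7.2.4, for example:

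> The trial stops if 2 patients each have at least one Clavien-Dindo grade 3 or higher adverse event within 30 days of surgery that is judged related to the bone marrow aspiration.

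Replace the stopping wording in 11.1.7, 12.1.4 and 12.2.2 with a cross-reference to it.

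The sponsor should also say in that rule whether possibly related events count. Counting them is more cautious. The price is that some complications of the operation itself, such as bleeding or infection at a shared incision, could count towards stopping. Either choice is defensible once it is written down. If the sponsor prefers an any-cause rule or a count of events, that too can be stated once in 7.2.4.

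The cost is an amendment of wording: one rule and three cross-references, with no extra patients, visits or data.

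A separate, minor correction can be made in the same amendment. Section 11.1.5 says "Adverse events will be followed up to four weeks postoperatively", whereas sections 6.1 and 12.1.2 use 30 days. Setting 11.1.5 to 30 days would make follow-up cover the window of the rule.
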